Metyrosine – common: drowsiness, diarrhea, drooling, trembling and shaking of hands and fingers; trouble speaking. Uncommon: decreased sexual ability in men, dry mouth, nausea, vomiting, stuffy nose, anxiety, confusion, hallucinations, mental depression. Rare or life-threatening: crystalluria (the excretion of crystals in the urine resulting in urine retention), black, tarry stools, unusual bleeding or bruising, muscle spasms, painful urination, pinpoint red spots on skin, restlessness, shortness of breath, shuffling walk, skin rash and itching, swelling of feet or lower legs, tic-like movements

L-Dopa (levodopa) – common: abdominal pain, dry mouth, loss of appetite, nightmares, gas, abnormal thoughts, agitation, anxiety, clumsiness, difficulty swallowing, dizziness, excessive watering of mouth, nausea and vomiting, uncontrolled body movements. Uncommon: Chest pain, mood or mental changes, discoloration of sweat or urine, constipation, diarrhea, flushed skin, headache, hiccups, increased sweating, muscle twitching, trouble sleeping, blurred vision, difficult urination, dilated pupils, dizziness or lightheadedness when getting up from a lying or sitting position, double vision, fast or pounding heartbeat, hot flushes, mental depression, skin rash, weight gain or loss. Rare: back or leg pain, black tarry stools, chills, convulsions, fever, high blood pressure, loss of appetite, swelling of feet or lower legs

Atomoxetine – common: headache, nausea, sleepiness, trouble sleeping, anxiety, dry mouth, loss of appetite, dizziness, constipation, flushed or warm sensation, rash. Uncommon: loose stools, excessive energy, excitement, stomachache ache, fluttering sensation in chest, abnormal heart rhythm sensations, tingling, vomiting, aching muscles. Rare: abnormal blood tests, such as abnormal liver function tests

L-DOPS – The use of L-DOPS is under investigation and is not approved by the FDA. We have used it for many years in a small population of patients that lack dopamine-beta-hydroxylase, the

enzyme that converts dopamine to norepinephrine. The initial dose is low and adjusted to treat low blood pressure without adverse effects. It is possible that there may be some side effects. The following rare side effects have been reported: increased blood pressure, nausea, headache, hallucination, anorexia, increased liver enzymes, dizziness/lightheadedness, heart fluttering, thirst, nervousness, stomachache, vomiting, abdominal pain, chest pain, and fatigue.

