Placebo – The placebo is a pill or capsule that does not contain active ingredient. It should therefore have no side effects.

PROTECTION:

Monitoring of vital signs will help minimize potential risks. All information will be kept strictly confidential.

BENEFITS:

We guarantee no direct benefits to the study participants. Results of this study will improve our understanding of autonomic dysfunction and might lead to important advances in the management of these diseases.

DATA SAFETY MONITORING PLAN

Data from subjects enrolled in this study will be reviewed on a bi-monthly basis by the P.I. and at least one co-investigator. Any adverse event of a serious or greater nature will be reviewed immediately with the P.I. [name]. will be responsible for tracking adverse events in this study.

The adverse event will be described with the following information: description of the event; outcome of the event; duration of the event; relationship to study procedure; requirement, if any, for treatment or intervention; and outcome.

Adverse events will be graded according to the following scale:

0 = No adverse event or within normal limits

1 = Mild adverse event (transient and mild in nature, and no treatment is necessary)

2 = Moderate adverse event (some intervention and treatment are necessary, but participant completely recovers)

3 = Severe adverse event (an event that results in hospitalization, disability, or death or is life-threatening)

The investigator will state his opinion on whether there is a reasonable possibility that the event or experience is related to a procedure performed as part of this study.

JUSTIFICATION FOR GCRC UTILIZATION

The following GCRC services are necessary for conducting this scientific study:

Inpatient/Outpatient Support: Approximately 25 patients will be studied over the five years. The length of stay and number of admissions will depend on the number of medication trials performed with each patient. A research nurse will be needed to draw blood and monitor blood pressure during pharmacological testing, to document pulse and blood pressure during orthostatic vital signs, to perform posture studies, and to assist with urine collections, as well as for general patient care.

Biostatistical Support: Although we do not anticipate doing any data analysis, review by the GCRC biostatistician is requested, as well as assistance with any unforeseen data analysis.

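### As written, the adverse-event scale gives no grade to three kinds of event below Grade 3, because Grade 1 requires a transient course and Grade 2 requires treatment with full recovery

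*Combined protocol and SAP*

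**What the plan says.** The scale stands in the Data Safety Monitoring Plan section of the combined protocol and SAP. It is introduced as a firm rule: "Adverse events will be graded according to the following scale". It has four levels:

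- The bottom level is kept for patients in whom nothing happened: "0 = No adverse event or within normal limits".
- The next one up joins course, severity and lack of treatment in a single definition: "1 = Mild adverse event (transient and mild in nature, and no treatment is necessary".
- The third level joins treatment to the final result for the patient: "2 = Moderate adverse event (some intervention and treatment are necessary, but participant completely recovers".
- The top level is defined by consequence alone, with no mention of course or recovery: "3 = Severe adverse event (an event that results in hospitalization, disability, or death or is life-threatening".

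No other grading rule appears, and none says what to do with an event that matches no level. Just before the scale, the same section lists what is to be recorded for each event: "description of the event; outcome of the event; duration of the event; relationship to study procedure; requirement, if any, for treatment or intervention; and outcome". Course, outcome and need for treatment are therefore collected apart from the grade.

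Exposure can be long. Under Experimental Design and Methods, patients may go on from the single-dose and 5-day trials to a trial of about two months, with evaluations at the start and after two, four and eight weeks of drug. Potential Risks lists side effects by drug and frequency class. For metyrosine it gives "common: drowsiness, diarrhea, drooling, trembling and shaking of hands and fingers; trouble speaking". Dry mouth is listed as common for domperidone, alpha-methyldopa and atomoxetine.

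**The concern.** A severity scale should place every event in exactly one level. This one makes duration part of Grade 1 and final outcome part of Grade 2, so an event can fail a grade for reasons unrelated to how severe it was.

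Take mild drowsiness that lasts as long as dosing continues and is not treated. It is not transient, so it is not Grade 1. It is not treated, so it is not Grade 2. It meets no Grade 3 criterion, and Grade 0 is for no event. A tremor that is treated and only partly resolves, without hospitalization or disability, fails Grade 2 on recovery and does not reach Grade 3. A brief hallucination judged more than mild but needing no treatment fails Grade 1 on severity and Grade 2 on treatment.

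The grader must then leave the grade blank or use one whose definition the event fails. Graders may choose differently, and with about 25 patients a few such choices could change any table by grade. This is the documents' only scale for harms.

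**Working it through.** The plan gives no figure to reproduce. The check applies the four definitions literally to every combination of attributes they mention.

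**Conditions, from the Data Safety Monitoring Plan**

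- Grade 0: no event, or within normal limits.
- Grade 1: transient AND mild AND no treatment needed.
- Grade 2: treatment needed AND complete recovery.
- Grade 3: any of hospitalization, disability, death or threat to life, whatever the treatment, duration or recovery.

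**Coarse count, events with no Grade 3 criterion**

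| Treated? | Course | Severity | Grade met |
|---|---|---|---|
| No | Transient | Mild | 1 |
| No | Transient | More than mild | none |
| No | Persistent | Mild | none |
| No | Persistent | More than mild | none |
| Yes | Fully recovered | any | 2 |
| Yes | Not fully recovered | any | none |

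Graded: 2 of 6. Ungraded: 4 of 6.

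**Finer count**

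Cross five yes/no attributes: mild, transient, treated, fully recovered, Grade 3 criterion met. That gives 2^5 = 32 combinations. Remove transient without recovery (8) and, from the rest, mild with a Grade 3 criterion (6). This leaves 32 − 8 − 6 = 18 types.

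- No Grade 3 criterion, 12 types: 1 is Grade 1, 4 are Grade 2 and 7 have no grade. The 7 are 4 persistent and untreated, 2 treated without full recovery, and 1 transient and untreated but more than mild.
- Grade 3 criterion met, 6 types: all meet Grade 3. Two of them (treated and fully recovered) also meet Grade 2.

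The counts agree. Merging the finer split's 4 + 2 + 1 ungraded types over attributes that the coarse table does not separate gives 2 + 1 + 1 = 4 cells.

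**Timing**

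Grade 2 depends on the final outcome. While a treated event below Grade 3 is still open, its recovery condition is not met, so the event has no confirmed grade. If it has not resolved by the last evaluation at eight weeks, Grade 2 is still not met.

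**Check of the proposed wording on the same 18 types**

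- Grade 1 (mild, no treatment needed, any duration): 3.
- Grade 2 (no Grade 3 criterion, and treated or more than mild): 6 treated + 3 untreated = 9.
- Grade 3 (unchanged): 6.

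3 + 9 + 6 = 18, so each type falls in exactly one grade.

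**The case against.** The best defence is that this is the strictest reading available. Each level opens with a label (mild, moderate, severe), and the bracketed text could be taken as description. A sensible grader would put persistent mild drowsiness under mild. Disability is undefined and might take in some lasting effects. No time for grading is set, so a grader could wait for the outcome. The information also survives: "outcome of the event; duration of the event" are on the list of recorded items, with need for treatment, so any event could be regraded later.

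Part of this stands. Nothing is lost from the record, and nothing says that an event without a grade is dropped. Persistent or unresolved events that meet a Grade 3 criterion are graded 3. But grading by label means overriding written conditions, and the plan gives no rule for doing so consistently.

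A reader might infer three stronger consequences. The documents do not support them:

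- **That the ungraded events are the expected harms of eight-week dosing.** Potential Risks classifies listed effects by frequency and does not say how long they last or whether patients recover fully. That common effects such as drowsiness or dry mouth could last while dosing continues is plausible, but not stated. Nothing suggests that incomplete recovery after treatment is expected. The two-month stage is conditional, and no particular drug is certain to reach it.
- **That a drug-versus-placebo comparison of harms is distorted.** The chronic schedule has no placebo period; placebo appears in the single-dose drug list and the 5-day crossover. Biostatistics speaks of comparing treatment responses within a subject, no table of harms by grade is specified, and the Biostatistical Support paragraph anticipates no data analysis.
- **That ungraded events wait for routine review.** Immediate review is triggered by an event being serious, a word that is not a label on the scale and is not tied there to Grade 3. Patients in the chronic stage also have symptoms assessed at two, four and eight weeks.

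**Conclusion.** The point holds in a limited form. The plan states a grading rule that cannot be followed for some events: four of six logical categories below Grade 3 match no level, and one combination above that line matches two. This is a defect in a stated rule, not a missing detail. It rests on reading the bracketed conditions as requirements, on taking a transient event to have resolved, and on taking a mild event to meet no Grade 3 criterion.

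The size is a count of categories and must not be read as a share of events. The documents give no event frequencies, and assuming a percentage would only return the percentage assumed. The damage is confined to the grade and to any summary by grade, and is most likely to arise in the two-month stage if patients reach it. It should be corrected, but it does not threaten the blood-pressure assessments or the record of harms.

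**What to change.** Let the grade depend on severity and need for treatment only:

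- **Grade 1:** delete the word transient, so that it covers any mild event needing no treatment, whatever its duration.
- **Grade 2:** delete the complete-recovery condition. Let it cover every event that meets no Grade 3 criterion and either needs treatment or is more than mild. This closes the gaps and removes the overlap with Grade 3.
- **Grade 3:** leave as it is.
- **Timing:** grade each event at its worst point, without waiting for resolution.
- **Reporting:** show duration and outcome, with not recovered as an explicit outcome, beside the grade from the fields already collected.

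The cost is a change to two lines of the scale, a sentence each on timing and reporting, and the matching entries on the adverse-event form. No new data or patients are needed, and treatment is unaffected. Slightly more events will be counted as Grade 1 or 2, so a summary by grade may look slightly less favourable.
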